**Information**

Title	France Zimino® registry: A French registry evaluating the use of Zimino
Protocol version	Final Version - V1_08.11.2019
Date of protocol	08 November 2019
Active substance	Levosimendan
Medicinal product	Zimino
Product reference	Not applicable
Procedure number	2019-A02903-54
Marketing authorisation holder (MAH)	Orion Corporation, Finland
Research question and objectives	To provide real-life follow-up data on patients who have been treated with Zimino® according to local routine clinical practice in France.
Country of study	France
Sponsor	ARCOTHOVA (Anesthésistes-Réanimateurs Cœur Thorax Vaisseaux)

## 2. LIST OF ABBREVIATIONS

ANSM	Agence Nationale de Sécurité du Médicaments et des Produits de Santé
CRF/eCRF	Case report form/electronic Case Report Form
EEC	External Electrical Cardioversion
EC	Ethics Committee
EDC	Electronic Data Capture
GCP	Good Clinical Practice
GPP	Good Pharmacoepidemiology Practices
IABP	Intra-Aortic Aalloon Pump
ICU/CCU	Intensive Care Unit /Coronary Care Unit
MACE	Major Adverse Cardiovascular Event
SAE	Serious Adverse Event
SAPS	Simplified Acute Physiology Score
SAS®	Statistical Analysis System
SOFA	Sequential Organ Failure Assessment
VA ECMO	Veno-Arterial ExtraCorporeal Membrane Oxygenation
VV ECMO	Veno-Venous ExtraEorporeal Membrane Oxygenation

#### **Investigators**

In this protocol ‘investigator’ refers to physician who is responsible for all treatment decisions and the conduct of the study at a study centre.

Signatures of the investigators will be collected in Annex 2.

## 4. ABSTRACT

Title France Zimino® registry: A French registry evaluating the use of levosimendan (Zimino®)

Protocol version and date V1, 08 November 2019

Rationale and background The French National Authority for Health (Haute Autorité de santé) requested a registry study to obtain post-market surveillance data to describe baseline clinical profiles, management and outcome of patients treated with Zimino®. This study is designed to provide real-life data on the use, safety and clinical outcomes of Zimino® in routine clinical practice in France.

Research question and objectives Primary objective:
 
 
• To provide real-life follow-up data on patients who have been treated with Zimino® according to local routine clinical practice in France.
 
 
Secondary objectives:
 
 
• To describe the use of concomitant inotropes during hospitalisation.
 
• To assess re-hospitalisations 30 and 90 days after hospital discharge.
 
• To evaluate tolerance and serious adverse events (SAEs) during hospitalisation.
 
• To assess mortality 30 and 90 days after hospital discharge.
 

Primary endpoints
 
 
• Indication for Zimino®.
 
• Dose and duration of treatment with Zimino®.
 
• Length of intensive care unit / coronary care unit (ICU/CCU) stay from the start of Zimino®.
 
• Length of hospital stay from the start of Zimino®.
 

Secondary endpoints
 
 
• Concomitant inotropes during hospitalisation.
 
• Re-hospitalisations 30 and 90 days after hospital discharge.
 
• Tolerance, as assessed by hypotension and atrial fibrillation during hospitalisation.
 
• SAEs, including major cardiovascular events (MACEs), mechanical assistance, dialysis or any other event engaging the vital prognosis during hospitalisation.
 
• Mortality during hospitalisation 30 and 90 days after hospital discharge.
 


Study design This is a real-life, non-interventional, observational, multicentre study in all patients (including children) receiving Zimino® in France. The patients will be evaluated during the index hospitalisation and on follow-up days 30 (±15) and 90 (±15) after hospital discharge. The follow-up can be a phone call or a visit to the hospital. Patients who meet the eligibility criteria will be identified consecutively at each hospital. The participating hospitals will vary in size and medical activities, depending on their location and the population size they serve. The physician will determine the patient's treatment strategy. Drug prescriptions and the indications to perform diagnostic or therapeutic procedures will be left completely to the discretion of the physicians. The estimated enrollment period is 12 months (enrollment of the first patient – enrollment of the last patient), or less if the cohort (n=600) is completed earlier, and the maximum total data collection period is 15 months.

Population
 
Inclusion criteria:
 
 
• Patients receiving Zimino® treatment.
 
• Patients or patient's families not objecting to the patient's participation in the study.
 
 
Exclusion criteria: None

Medicinal product, dose and mode of administration
 
Zimino® 2.5 mg/ml concentrate for solution for infusion. Dose and duration of treatment will be at the discretion of the physicians.


Variables
 
 
• Demographic characteristics, including age and sex
 
• Dates of hospital and ICU/CCU admission and discharge
 
• Reason for hospitalisation.
 
• Cardiogenic shock (yes/no; if yes, date of the first symptoms)
 
• Zimino® prescription, including indication for use, dose and duration (date and hour), bolus (yes/no).
 
• Concomitant inotropes: drug name, dose, duration (date and hour)
 
• Chronic atrial fibrillation (yes/no)
 
• Pre-existing amiodarone before the start of Zimino® (yes/no)
 
• Pre-existing betablockers before the start of Zimino® (yes/no) and higher dose
 
• Pre-existing dialysis before the start of Zimino® (yes/no) 
 
- Start date
 
- Date of weaning (or death)
 
 
 
• Pre-existing mechanical assistance before the start of Zimino® 
 
○ Venoarterial extracorporeal membrane oxygenation (VA ECMO) (central or peripheral)
 
○ Veno-venous ECMO (VV ECMO)
 
○ Impella® 5.0 or Impella® 2.5 or Impella CP
 
○ Intra-aortic balloon pump (IABP)
 
○ Berlin Heart EXCOR
 
 
For all the assistances collect :
 
 
- Start date of mechanical assistance
 
- Date of assistance weaning (or death)
 
 
 
• Tolerance information during the levosimendan infusion including: 
 
○ Hypotension 
 
- Catécholamines (yes/no) if yes : Start date/ stop date
 
- Zimino® reduced (yes/no) or Interrupted (yes/no) or Discontinued (yes/no)
 
 
 
○ New atrial fibrillation 
 
- Need for amiodarone (yes/no)
 
- Need for cardioversion (yes/no)
 
 
 
 
 
• SAEs after the start of Zimino®: 
 
○ MACEs, defined as death of cardiac origin, stroke, myocardial infarction, heart rhythm disorder requiring cardioversion or cardiogenic pulmonary oedema
 
○ Death of other cause
 
○ Mechanical assistance 
 
- VA ECMO (central or peripheral)
 
- VV ECMO
 
 
 
 
 


 
- Impella® 5.0 or Impella® 2.5 or Impella CP
 
- IABP
 
- Berlin Heart EXCOR
 
 
 
- Start date of mechanical assistance
 
- Date of assistance weaning (or death)
 
 
 
○ Dialysis             
 
- Start date
 
- Date of weaning (or death)
 
 
 
○ Any other event engaging the vital prognosis during hospitalisation, including septic shock and digestive haemorrhage
 
 
 
● Mortality during hospitalisation and up to follow-up days 30 and 90 after hospital discharge.
 
● Re-hospitalisations up to follow-up days 30 and 90 after discharge, including number and duration of re-hospitalisations, main reason for re-hospitalisation and re-administration of Zimino®
 

Data sources
 
Data will be collected from medical records and follow-up interviews and entered into the electronic case report forms (eCRFs).
 
Data before admission to the hospital and during hospitalisation will be obtained during index hospitalisation. The prospective follow-up data will be obtained on days 30 and 90 after discharge by calling the patient or patient’s family or during the patient’s visit to the hospital. Follow-up data will also be collected from medical records.

Study size
 
600 patients will be included in the registry.

Data analysis
 
The objective of the study is to provide real-life follow-up data in patients who received Zimino®. There is no formal hypothesis to be tested. All enrolled patients who have received Zimino® will be included in the analysis. All variables will be summarised overall and by indication for the use. For categorical variables proportions and 2-sided 95% confidence intervals will be presented. If applicable, the potential differences between indications of Zimino® will be tested. Additional subgroup analyses may be performed based on the observed data.

Milestones
 
Data collection for the main study is expected to start by January, 2020 and to be completed before December 31th, 2020.

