## 8. RESEARCH QUESTION AND OBJECTIVES

In this real-life, multicentre study, patients treated with Zimino® will be followed for 90 days after discharge from the hospital

The primary objective is to provide real-life follow-up data on patients who have been treated with Zimino® in France.

The secondary objectives are:

- To describe the use of concomitant inotropes during hospitalisation.
- To assess re-hospitalisations at 90 days after discharge.
- To evaluate tolerance and serious adverse events (SAEs) during hospitalisation
- To assess mortality during hospitalisation and at 30 and 90 days after discharge.

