### **9.3.9 Mortality**

Time of death and cause of death will be recorded up to follow-up day 90.

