### 9.3.11 Re-hospitalisations up to 30 ( $\pm 15$ ) and 90 ( $\pm 15$ ) days after hospital discharge

- Was the patient re-admitted to the hospital (yes or no)
- If yes: date of admission
- If yes: date of discharge
- Main reason for re-hospitalisation
- Re-administration of Zimino® (yes/no)

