### **9.7.3 Statistical analyses**

The variables will be evaluated by frequency tables and summary statistics, as applicable. Variables will be summarised also by indication for the use, if feasible. For categorical variables, proportions and 2-sided 95% confidence intervals will be presented.

For the primary objective, all clinical and sociodemographic characteristics (age, sex, clinical scores) use of Zimino treatment (indication, dose, duration, routes) will be described at each available time point.

For secondary objectives, use of concomitant inotropes during the hospitalisation (percentage of patient, duration etc...) will be described, as well as rate of patient rehospitalised at 90 days after discharge.

For safety and tolerance analysis, description of hypotension, new atrial fibrillation will be done as well as all SAEs occurred during and after Zimino® treatment.

Rate of mortality will be calculated and described.

If applicable, the potential differences between indications of Zimino® will be tested in an exploratory way, as no statistical hypothesis have been done. Additional subgroup analyses may be performed based on the observed data.

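### Section 9.3.11 builds the ±15-day contact tolerance into the re-hospitalisation variable, and a compliant last contact before day 90 leaves up to 15 days without scheduled observation

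*Protocol*

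**What the plan says.** The Abstract (Study design) places the two post-discharge contacts within a tolerance: "The patients will be evaluated during the index hospitalisation and on follow-up days 30 (±15) and 90 (±15) after hospital discharge". Table 1 in section 9.2.4 uses the same ±15 days as column labels. In both places it describes when the patient is contacted.

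For re-hospitalisation the Protocol gives two versions of the variable. The heading of section 9.3.11 reads "Re-hospitalisations up to 30 ( $\pm 15$ ) and 90 ( $\pm 15$ ) days after hospital discharge". The Abstract (Variables) reads "Re-hospitalisations up to follow-up days 30 and 90 after discharge, including number and duration of re-hospitalisations", with no tolerance. Under 9.3.11 the items are a yes/no on re-admission followed by dates, beginning with "If yes: date of admission". The analysis named in section 9.7.3 is the "rate of patient rehospitalised at 90 days after discharge".

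For mortality no definition carries the tolerance. The Abstract has "Mortality during hospitalisation and up to follow-up days 30 and 90 after hospital discharge", section 8 has "To assess mortality during hospitalisation and at 30 and 90 days after discharge", and section 9.3.9 has "Time of death and cause of death will be recorded up to follow-up day 90".

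Section 9.3.10 also lists hospital-free days at day 30 and day 90, again with no tolerance.

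On medical records as a follow-up source, the Abstract (Data sources) says they will be used, whereas section 9.2.4 says only that they may be.

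**The concern.** A contact window and a counting period are different things. The first says when someone telephones; the second says over how many days an event counts. If the tolerance becomes part of the variable, patients are counted over unequal lengths of time and the reported figure is no longer a 30-day or 90-day rate.

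There is also a data-collection problem that does not depend on how the heading is read. The day-90 contact is the last one scheduled. A site that calls on day 75 has complied with the Protocol, and nothing further is required of it, yet the remaining days to day 90 have not been observed. If such a patient is entered as event-free at day 90, the rate is biased downwards. An analysis plan can cut off events that were recorded too late, but it cannot recover days that nobody asked about.

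The outcomes concerned are secondary endpoints: re-hospitalisation and mortality after discharge.

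**Working it through.** **Inputs from the Protocol.** Contacts at 30 ± 15 and 90 ± 15 days after discharge (Abstract; Table 1). Admission and discharge dates of re-hospitalisations (9.3.11) and time of death (9.3.9) are recorded. Precision target 4.5 percentage points at a proportion of 50% (9.5). The Protocol gives no expected re-hospitalisation or death rate, so the risks below are assumptions, shown as a range.

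**The plan's own figure, used only as a yardstick.** n = 1.96² × 0.25 / 0.045² = 474.3, rounded up to 475, as in section 9.5. The point does not alter the sample size.

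**Step 1: the literal counting periods.**
- Day 30: 30 − 15 = 15 to 30 + 15 = 45 days, a ratio of 45/15 = 3.0.
- Day 90: 90 − 15 = 75 to 90 + 15 = 105 days, a ratio of 105/75 = 1.4.

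**Step 2: which parts the recorded dates can repair.**
- Contact on days 31–45 or 91–105: later events can be removed by their date.
- Day-30 contact made on days 15–29: the missing days can be completed at the day-90 contact.
- Day-90 contact made on days 75–89: no later contact is scheduled. Between 1 and 15 days stay unobserved unless records are consulted.

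Only the third case is a loss that dates alone cannot repair. It applies to re-hospitalisation and to death.

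**Step 3: size at day 90.** Assume a constant hazard. With true 90-day risk R, λ = −ln(1 − R)/90, and the risk seen by day t is 1 − exp(−λt) = 1 − (1 − R)^(t/90).

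For R = 30%: λ = 0.003963.
- All last calls on day 75: 1 − 0.7^(75/90) = 25.7%.
- All on day 105 with no cut-off by date: 1 − 0.7^(105/90) = 34.0%.
- Contacts uniform over days 75–105, events cut off at day 90, no help from records. Half the patients are followed to day 90 and read 30%. The other half have last contacts uniform over days 75–90, with mean reading 1 − [exp(−75λ) − exp(−90λ)]/(15λ) = 1 − 0.042874/0.059446 = 27.9%. The average is (30.0 + 27.9)/2 ≈ 28.9%.

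| True 90-day risk | All last calls day 75 | Uniform 75–105, date cut-off | All day 105, no cut-off |
|---|---|---|---|
| 20% | 17.0% | 19.3% | 22.9% |
| 30% | 25.7% | 28.9% | 34.0% |
| 40% | 34.7% | 38.7% | 44.9% |

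The downward error is 3.0, 4.3 and 5.3 points at the day-75 extreme, and 0.7, 1.1 and 1.3 points with uniform contacts.

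**Step 4: hospital-free days.** If day 90 is counted from discharge, a last contact on day 75 leaves 15 of the 90 days unknown. Section 9.3.10 measures length of stay from the start of Zimino. If hospital-free days are counted from there too, the gap is shorter by the length of stay after starting treatment.

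**The case against.** The strongest reply is that the tolerance is only a visit window. The Abstract and Table 1 use it that way, the 9.3.11 heading can be read as naming the two visits, and the Abstract's own definition has no tolerance. Because admission dates and time of death are collected, an analysis plan can cut off at day 30 and day 90, and an early day-30 call is completed at the later contact. This stands. It removes any claim that the data must span a threefold range at day 30: that range arises only if the recorded dates are ignored.

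A reader might infer that 30- and 90-day mortality are likewise counted over 15–45 and 75–105 days. The documents do not support that. The Abstract and sections 8 and 9.3.9 all name fixed days. The Abstract does attach ±15 to the phrase follow-up days, which leaves a little ambiguity, but no mortality definition includes it.

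A reader might also infer that events between an early last call and day 90 can never be seen. That goes too far. Records are a stated source, and for transferred patients the receiving hospital is contacted. However, the Protocol says both that records will and that they may be used, and nowhere requires a check through day 90 after an early call. For patients discharged home or to another care facility, section 9.2.4 relies on the patient or family. Records may also miss admissions elsewhere.

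Finally, the extremes put every call at one edge, and nothing in the Protocol shows that call timing differs by indication. Both objections are fair; a mixture of contact days gives the smaller errors.

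**Conclusion.** The point holds in a limited form. Section 9.3.11 and the Abstract disagree on whether the tolerance belongs to the re-hospitalisation variable, and they should be reconciled. Separately, the Protocol allows follow-up to end on days 75–89 with no requirement to establish status through day 90. This affects re-hospitalisation, mortality and, depending on where day 90 is counted from, hospital-free days. Section 9.3 lists no contact date or date last known alive, so its variables do not distinguish a patient event-free to day 90 from one last heard of on day 75. The eCRF itself was not available to check.

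For a true 90-day risk of 30%, the understatement is about 1.1 points with uniform contacts and 4.3 points if every last call is on day 75. Both assume a constant hazard and no help from records. The larger figure is close to the 4.5-point precision target. The smaller is well inside it, but it is bias, which a larger enrolment does not reduce. In a descriptive registry with no confirmatory hypothesis this is worth correcting because it is cheap; it does not threaten the study. Whether a separate analysis plan already applies a date cut-off cannot be seen, and such a plan could not supply the unobserved days.

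**What to change.** 1. Remove the ±15 from the 9.3.11 variable. Count re-admissions and deaths on or before exactly day 30 and day 90 after discharge, using the dates already collected, and leave later events out of those rates.
2. Keep the tolerance in section 9.2.4 and Table 1 as a contact window only. Require status to be ascertained through day 90, either by a final contact on days 90–105 or, after an earlier call, by a record check or short re-contact at or after day 90. Make the Abstract and section 9.2.4 agree on whether record review is required.
3. Record the date of last contact or last known alive. Treat a living patient not followed to day 90 as censored at that date, not as event-free.
4. State in 9.3.10 from which date hospital-free days are counted.

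The cost is a wording amendment, one extra date field, and somewhat later final contacts (or a brief second check) for patients called early. Day 105 is already the upper limit. The timing must be checked against the limit of 15 months' total data collection with 12 months' enrolment (Abstract; section 9.1). A patient enrolled at the end of month 12 has 15 − 12 = 3 months left to cover both the rest of the index stay and the follow-up. The present day-105 limit already strains that cap, and requiring status through day 90 removes the early calls that fit it most easily.

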### **9.2.4 Study procedures**

The prospective follow-up data will be obtained on days 30 and 90 after discharge by calling the patient or a patient's family member, or during a visit to the hospital if the patient is hospitalized or comes for a scheduled consultation. Follow-up data may also be obtained by review of medical records.

For patients who have been transferred to another hospital, follow-up data will be collected by contacting the respective hospital according to local practice. For patients who have been discharged home or to another care facility, follow-up data will be collected by contacting the patient or the patient's family. Every effort will be made according to local practice to ensure that the patient is alive before contacting the patient's family.

Table 1 lists study procedures and indicates with an 'x' during which visit a particular procedure is performed.

Table 1. Schedule of study procedures

	During index hospitalisation	During follow-up	
		30 ( $\pm$ 15) days after discharge	90 ( $\pm$ 15) days after discharge
Patient identification	x		
Informed consent	x		
Inclusion criteria	x		
Demographic characteristics	x		
Hospital and ICU/CCU admission dates	x		
Reason for hospitalisation	x		
Cardiogenic shock	x		
Zimino® treatment	x		
Concomitant inotropes	x		
Chronic atrial fibrillation	x		
Pre-existing amiodarone	x		
Pre-existing dialysis	x		
Pre-existing mechanical assistance	x		
Tolerance	x		
SAEs	x	x	x
Mortality	x	x	x
ICU/CCU and hospital discharge dates	x		
Re-hospitalisations		x	x

ICU = Intensive care unit; CCU = Coronary care unit; SAE = Serious adverse event

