### 9.3 Variables to be collected

Data will be collected for all patients and recorded on the CRFs as follows:

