#### **9.3.7 Tolerance**

- Hypotension during and after the start of Zimino® (yes/no).
  - If yes, was noradrenaline started or its dose increased? (yes/no).
  - Duration of hypotension (minutes, hours)

- New atrial fibrillation after the start of Zimino® (yes/no)? If yes,
  - Was amiodarone given? (yes/no).
  - Was beta-blocker given ? (yes/no)
  - Was cardioversion performed?
  - Persistent AF? (yes or no)
  - If transient, duration of AF (min, hours, days)

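### The tolerance endpoint has conflicting time windows and field lists, and section 9.3.7 neither dates the events nor separates hypotension already present at the start of Zimino

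*Protocol*

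**What the plan says.** Four places in the protocol bear on when tolerance is observed.

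- Section 4 (Abstract), Variables: "Tolerance information during the levosimendan infusion including" hypotension and new AF. Under hypotension it lists catecholamines (with start and stop dates if given) and whether Zimino was reduced, interrupted or discontinued.
- Section 4 (Abstract), Secondary endpoints: "Tolerance, as assessed by hypotension and atrial fibrillation during hospitalisation". The section 8 objective agrees: "To evaluate tolerance and serious adverse events (SAEs) during hospitalisation".
- Section 9.2.4, Table 1, which shows "during which visit a particular procedure is performed", marks tolerance for the index hospitalisation and for neither follow-up contact.
- Section 9.3.7 asks "Hypotension during and after the start of Zimino® (yes/no"), then "If yes, was noradrenaline started or its dose increased? (yes/no") and "Duration of hypotension (minutes, hours"). New AF is asked as yes/no after the start of Zimino, with treatment given, persistence and, if transient, duration.

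Section 9.3 introduces its lists with "Data will be collected for all patients and recorded on the CRFs as follows", so section 9.3.7 is the protocol's statement of what the CRF holds on tolerance. Section 9.7.3 then promises a description of hypotension and new AF.

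**The concern.** Hypotension and new AF are the named tolerance endpoint of a registry whose rationale includes real-life safety data. A site working from the abstract's variable list would answer yes only for events during the infusion. A site working from section 9.3.7 would also count events days later. The two sets of answers would then be pooled as one proportion.

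Two features of section 9.3.7 make this hard to repair afterwards. There is no onset time, so a yes cannot in general be placed inside or outside the infusion. Hypotension is also not asked as new, so a patient who was hypotensive before Zimino and stayed so can count as a tolerance event. Sections 4 and 9.7.3 allow differences between indications to be tested. If patients in one indication are more often hypotensive at the start, such a difference may reflect their starting state rather than tolerance.

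**Working it through.** The plan states no figure to reproduce, so the check sets the passages side by side.

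**Step 1: windows.**

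| Place | Window starts | Window ends |
|---|---|---|
| Section 4, Variables | start of infusion | end of infusion |
| Section 4, Secondary endpoints; section 8 | admission, if read literally | discharge |
| Section 9.3.7, hypotension and new AF | start of Zimino | not stated |
| Section 9.2.4, Table 1 | index stay | index stay |
| Section 9.7.3 | none given for these two events | none given |

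Table 1 does not discriminate: a mark for the index stay fits an infusion window and a window to discharge equally well. No place states start of Zimino to index discharge in full, but it is the reading closest to the endpoint, the objective and section 9.3.7 taken together.

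**Step 2: hypotension sub-fields.** The abstract has 3 Zimino-change fields; section 9.3.7 has 0 of them. The abstract has catecholamines with dates; section 9.3.7 has noradrenaline started or increased, undated, and adds duration. The change fields are yes/no, so they would place an event within the infusion only when a change was made.

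**Step 3: onset.** Section 9.3.2 records the start and stop of Zimino by date and hour. Placing an event in the infusion needs start ≤ onset ≤ stop. Section 9.3.7 gives an onset for 0 of its 2 events, and duration alone does not settle the inequality.

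**Step 4: starting state.** AF is asked as new, and section 9.3.4 records chronic AF. Hypotension has neither safeguard, while cardiogenic shock is the first indication listed in section 9.3.2.

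**Step 5: what other fields recover.**

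- Section 9.3.1: cardiogenic shock yes/no with the date of first symptoms. There is no hour, and a shock label is not a blood pressure at the start of Zimino.
- Section 9.3.2: SOFA score on the day of initiation. It is listed as a score and does not isolate hypotension.
- Section 9.3.3: noradrenaline start date and hour. A later dose increase is undated, because only the maximal dose is kept.
- Section 9.3.8: start dates, but only for events that qualify as SAEs, such as a rhythm disorder needing electrical cardioversion.
- Sections 4 and 9.7.3: summaries by indication (section 9.7.3 adds the condition that this be feasible). These set the cardiogenic shock indication apart but do not separate old from new hypotension within it.

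**Step 6: could the window matter?** This is an illustration only; its inputs are assumptions, not taken from the protocol. With a constant hazard h per day, the proportion with an event by day T is 1 − exp(−hT).

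| h per day | T = 1 day | T = 7 days | T = 14 days |
|---|---|---|---|
| 0.01 | 1.0% | 6.8% | 13.1% |
| 0.05 | 4.9% | 29.5% | 50.3% |

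If events cluster in the infusion instead, the gap between windows shrinks. The table shows that the choice can matter, not how much it does here.

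**The case against.** The strongest reply is that this is a descriptive registry with no hypothesis to test, that tolerance is a secondary endpoint, and that the mismatch may be no more than loose drafting in an abstract. The hospitalisation contains the infusion, so the passages need not be far apart. Data come from medical records, the eCRF is not shown, and section 5 foresees a pilot e-CRF and a possible amendment. The by-indication summaries and recorded shock status already set apart many of the patients most likely to start hypotensive.

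Much of this stands as mitigation. A reader might infer that the abstract's variable list is plainly the one mistaken passage. The documents do not go that far: Table 1 fits either window, section 9.3.7 has no stated end, and the choice belongs to the sponsor. A reader might also infer that the abstract's extra fields will not be collected. They are protocol text too, so this is a discrepancy to reconcile and not proof of absence. Nor is it right that section 9.3 times every drug while timing no tolerance event: amiodarone and beta-blockers are yes/no items without dates.

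What the reply does not remove is the conflict itself. Nor does description make the missing fields harmless, since description is the registry's purpose. A later analysis plan can choose a window, but it cannot rebuild from the CRF an onset time that the CRF did not hold; that would mean returning to the records.

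**Conclusion.** The point holds as a conflict between stated windows and between field lists, together with a gap in section 9.3.7 that leaves infusion-period events and new hypotension identifiable only in part. It deserves correction, though it does not threaten the registry as a whole.

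The size of the effect on the reported rates cannot be derived, because the protocol gives no tolerance rates, no infusion lengths and no share of patients hypotensive at the start. What can be counted is 0 of 2 tolerance events with an onset time in section 9.3.7, and 0 of the abstract's 3 Zimino-change fields carried into it. The conclusion assumes that the CRF follows section 9.3, as that section says. If the eCRF already holds onset times and a baseline item, only the wording needs repair.

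**What to change.** **Reconcile the text.** State one tolerance window, with a start and an end, in the abstract's variable list, the abstract's secondary endpoint, section 8 and section 9.3.7. Start of Zimino to index discharge is the closest reading of the last three; the sponsor should confirm what was intended. Bring the hypotension sub-fields of the abstract and section 9.3.7 into one list (catecholamines with dates or noradrenaline only; Zimino reduced, interrupted, discontinued).

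**Add three fields to section 9.3.7.**

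1. Hypotension already present at the start of Zimino, yes/no.
2. Date and hour of first onset of new hypotension, for patients not hypotensive at the start. For the others, record either the baseline flag alone or a new episode under a written definition; otherwise first onset has no meaning for them.
3. Date and hour of first onset of new AF.

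**Report accordingly.** Give hypotension with and without patients already hypotensive at the start. Derive the infusion-period rate from the start and stop times in section 9.3.2, noting that interruptions are not timed and that section 9.3.2 lists one start and one stop even though repetitive use is an indication.

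**Cost.** Two date/hour fields, one yes/no field and wording in four places, with no extra patients or visits. It is cheapest before enrolment, and the pilot foreseen in section 5 is a natural occasion. Data entry grows slightly, and episodes after the first remain untimed.
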